Will pregnant women and/or fetuses (as described in 45 CFR 46 Subpart B) be enrolled in the research? No

E4. Neonates

Will neonates of uncertain viability or nonviable neonates (as described in 45 CFR 46 Subpart B) be enrolled in the research?

E5. Children

Will children be enrolled in the research?

Section F: Design/Procedure

F1. Design

Select one category that most adequately describes your research:

c) Pilot

Discuss the research design including but not limited to such issues as: probability of group assignment, potential for subject to be randomized to placebo group, use of control subjects, etc.

This study will be a 4 weeks prospective (or up to wound healing or surgical revision, whichever came first), experimental study with N=60 consecutive patients, who are undergoing surgical closure.

Subjects will be randomized to either control or intervention group. The intervention group will receive the OxyGeni device and place the oxygen delivery within SOC dressing. The control group will receive standard of care wound dressing.

All patients will have baseline assessment including visual, dermal, neuropathy (Vibration Perception Threshold) and vascular assessment (ABI and Skin Perfusion Pressure). Then, the status of wound closure and presence of wound complication will be monitored every week. Each subjects will need up to 5 visits including baseline assessment, and weekly assessment up to 4 weeks or full wound healing or surgical revision, whichever came first, and an additional follow-up visit at a minimum 6 months after the surgery. At each visit, patients will be provided standard of care treatment including physical assessment, debridement and offloading. Table 1 in attachments' section summarizes the key measurement at each study visit.

Please note that no screening activities will take place prior to the patient signing a consent form.

Inclusion Criteria:

18-85 years of age. Ability to provide informed consent. Presence of a wound due to surgical intervention and closure. Subject or responsible caregiver is willing and able to maintain the required offloading (as applicable for the location of the wound) and applicable dressing changes

Exclusion Criteria:

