Medical History: The presence of diabetes will be based on American Diabetes Association criteria if applicable. This will include: duration and type of diabetes, type of diabetes medication (insulin, oral, combination therapy, diet), previous history of foot ulcers, amputation (toe, foot), lower extremity bypass, lower extremity angioplasty, Coronary artery bypass surgery, cardiac angioplasty, arthritis, liver disease, osteoporosis, malignancy, and bone tumors. We will use the Kaplan comorbidity index to record disease severity. We will measure height and weight to determine body mass index (BMI). We will evaluate and record glycated hemoglobin, albumin and prealbumin at baseline only in those patient charts where it is available due to the patient's standard of care treatment. Lab results will only be obtained only at the Baseline visit. Please note that patients will be recruited from an existing clinic population where they are already receiving Standard of Care procedures. These results will be obtained from your medical record at screening/baseline visit.

Social Factors: We will evaluate the following factors: marital status, years of education, type of work, tobacco history (pack years, current smoker, current use of chewing tobacco, previous smoker, no tobacco history), drug history (current, previous history, no drug history), and alcohol history. These factors will be collected at screening/baseline visit.

Peripheral Neuropathy: We will use Vibration Perception Threshold (VPT) Testing. VPT will be evaluated at the distal great toe, heel and 5th metatarsal head using a Biothesiometer. (Measurements will be done on screening/baseline visit and visit 4)

Heart Rate Monitoring: Zephyr BioHarness is an FDA approved wearable sensor which monitors physiological signs such as heart rate (electrocardiograph), breathing rate, skin temperature, and physical activity. This device will be comfortable placed on the sternum attached with either with two electrocardiograph (ECG) electrodes or elastic straps for subjects that report sensitive skin. Researchers will attach this device on the subject only for the duration of the visit. (Measurements will be done at all visits).

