Vascular Assessment: We will assess perfusion of the macro-circulation with arterial Doppler studies and micro-circulation with Skin Perfusion Pressure measurements and Ankle Brachial Index (ABI) will be measured on both extremities. Therefore, we will use the SensiLase system (Väsamed) to measure Skin Perfusion Pressure (SPP) in mmHg. The SensiLase is a device that will record the amount of Skin Perfusion Pressure. (Measurements will be done at screening/baseline visit and visits 2 & 4). We will also obtain oxygen tissue saturation images using Kent Camera or HyperView Camera (every visit)

-Ankle-Brachial Index: This test is to measure blood pressure of the ankle and arm while the subject is at rest. (Measurements will be done on screening/baseline visit and visits 2 & 4). Research Staff will: 1. Attach correct sized cuff on ankle and arm 2. Doppler probe will be placed on ankle and arm. 3. Cuffs will be inflated above your blood pressure. 4. The cuffs will deflate 5. Research Staff will document values in the subjects records. 6. Research Staff will remove the cuffs from the subjects ankle and arm.

-Skin Perfusion Pressure: This test will help the physician and researchers know if the tiny blood vessels in the subjects feet are blocked, damaged or if wound are getting enough blood to heal properly. (Measurements will be done on screening/baseline visit and visits 2 & 4) Research Staff will: 1. Ask the subject to lie flat 2. Research staff will place correct

sized pressure cuffs around the subjects ankles. 3. Research staff will also place an adhesive pad along with a sensor as (sensors will not be touching the skin directly) it will measure Skin Perfusion. 4. The cuffs will inflate above systolic blood pressure. 5. Research Staff will document values in the subjects record 6. Research Staff will remove cuffs from the ankle.

Adverse Event Reporting: Research Staff will document and report any study/non study related incident as per institution regulations. (Subjects will be asked on screening/baseline visit and visits 1- 4 and at the optional 5 visit).

Wound Assessment: A digital photo/video and thermal photo of wound will be taken for wound size verification and evaluate the area of inflammation. (Measurement will be performed at every visit). Photo may be taken with digital camera, KENT NIR camera, or eKARE camera.

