This is a pilot study. We plan to recruit a convenient sample of 60subjects (30 subjects per group), which we anticipate to be sufficient to observe a trend between groups to examine proof of concept of EO2 OxyGeni oxygen to reduce the likelihood of wound complication post-surgical wound closure. Based on our initial prevalence chart review, we anticipate that 20-30% of patients in the control group will have failure in wound closure (e.g. necrosis, tissue necrosis and its volume, infection, surgical revision). We anticipate to reduce the incident of wound complication to less than 5%. Using a chi-square test and assuming an alpha level of 5%, and ratio risk reduction of 25%, we anticipate to have statistical power of 95% using a 30 sample per group.

Based on this pilot study, we will calculate power and will design a clinical trial accordingly.

G2. Data Analysis

Provide a description of your plan for data analysis. State the types of comparisons you plan (e.g. comparison of means, comparison of proportions, regressions, analysis of variance). Which is the PRIMARY comparison/analysis? How will the analyses proposed relate to the primary purposes of your study?

The primary outcome of this study is the percentage of wound complication incidents post surgical interventions. We will use chi-square to estimate whether the number of wound complication incidents is less in the intervention group compared to the control group. The secondary outcomes of this study are: improvement in skin perfusion and reduction in perceived pain, anxiety, and stress. We will use general linear model (GLM) univariate analysis (UNIANOVA) to examine significant difference between groups for the secondary parameters of interest. Results will be adjusted by demographic information (age, gender, BMI) and clinical information (size of initial wound, A1C level, baseline skin perfusion).

Section H: Potential Risks/Discomforts

H1. Potential Risks/Discomforts

Describe and assess any potential risks/discomforts; (physical, psychological, social, legal, or other) and assess the likelihood and seriousness of such risks:

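### Does adjusting the secondary models for A1C lose patients, when the procedures record A1C only if the chart holds it?

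*Combined protocol and SAP*

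**What the plan says.** G2 names a univariate general linear model for the secondary outcomes. It adjusts for three demographic variables (age, gender, BMI) and for "clinical information (size of initial wound, A1C level, baseline skin perfusion". It does not say what happens when a covariate is missing. The primary outcome, the complication rate, is compared by a chi-square test with no covariates.

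Three of the four measured covariates come from study procedures in F2:

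- BMI: "We will measure height and weight to determine body mass index (BMI".
- Skin perfusion: "The SensiLase is a device that will record the amount of Skin Perfusion Pressure. (Measurements will be done at screening/baseline visit".
- Wound size: "A digital photo/video and thermal photo of wound will be taken for wound size verification".

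A1C differs. The Medical History paragraph of F2 states: "We will evaluate and record glycated hemoglobin, albumin and prealbumin at baseline only in those patient charts where it is available". It attributes availability to the patient's standard care, gives the medical record as the source, and adds: "Lab results will only be obtained only at the Baseline visit". Section L (Cost/Payment) lists, among standard-of-care items billed to insurance, an HbA1c at visit 0 for a patient whose electronic record has no earlier value.

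**The concern.** Someone reading G2 beside the Medical History paragraph sees a covariate that may be absent for some patients and no instruction for that case. The eligibility wording in F1 makes absence plausible. It asks for "Presence of a wound due to surgical intervention and closure" and does not require diabetes, so some patients may have had no reason for a routine A1C. The visit 0 test in Section L is not repeated in the F2 study tasks or in the baseline visit list.

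Standard software fits a linear model to complete cases unless told otherwise. A patient randomised, followed and measured on perfusion or pain could then drop out of the adjusted comparison for want of one baseline laboratory value. Intervals would widen, the results would describe only patients with an A1C, and the analysed set might be chosen after the data are seen.

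**Working it through.** **Step 1. Is A1C missing by design?** Set the two sections side by side.

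- F2, Medical History: A1C is recorded at baseline where the chart has it through standard care, and the source is the medical record.
- Section L: HbA1c is a standard-of-care item at visit 0 when the electronic record has no value.

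These are compatible. A test ordered as standard care at visit 0 would itself enter the medical record and could be taken from there at baseline. Together they read: use the chart value, otherwise test at visit 0. On that reading the missing share by design is 0%. The documents give no other figure for it.

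**Step 2. What would a loss require?** Two conditions must both hold: some patients have no A1C, and the model is run on complete cases. The first is not established (step 1). The second is a software default, not a statement in the plan.

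**Step 3. What would it cost if both held?** The plan has no figure of its own on this point; its 95% power claim concerns the unadjusted primary test and does not enter. The inputs are 60 patients, 30 per group (G1), and 8 parameters: intercept, group and the six covariates. The missing share f is an assumption. With N = 60(1 − f) and residual df = N − 8, the half-width of the 95% interval for the group difference, in residual SDs, is t(0.975, df) × √(4/N).

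| f (assumed) | N | df | t | Half-width | Ratio to f = 0 |
|---|---|---|---|---|---|
| 0% | 60 | 52 | 2.007 | 0.518 | 1.000 |
| 10% | 54 | 46 | 2.013 | 0.548 | 1.057 |
| 20% | 48 | 40 | 2.021 | 0.583 | 1.126 |
| 30% | 42 | 34 | 2.032 | 0.627 | 1.210 |
| 50% | 30 | 22 | 2.074 | 0.757 | 1.462 |

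For example, at f = 20%: 2.021 × √(4/48) = 0.583, and 0.583/0.518 is about 1.13. The formula ignores chance imbalance in the covariates. A simulation that includes it gives ratios of about 1.14 at 20% missing and 1.57 at 50%. Sixty is also an upper limit on evaluable patients, since F1 provides for "weekly assessment up to 4 weeks or full wound healing or surgical revision, whichever came first".

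**Step 4. What would an analyst's ordinary choices cost instead?** Let r² be the share of otherwise unexplained outcome variance due to A1C, assumed to be 0.1 or 0.2.

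- *Fill in the mean and add a missing indicator.* N stays at 60, with 9 parameters and 51 df. The residual SD rises by √(1 + f·r²/(1 − r²)). Including the change in t, the width ratio runs from 1.012 (f = 20%, r² = 0.1) to 1.061 (f = 50%, r² = 0.2).
- *Leave A1C out.* N stays at 60, with 7 parameters and 53 df. The residual SD rises by 1/√(1 − r²), which is 1/√0.9 = 1.054 or 1/√0.8 = 1.118, whatever f is.

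So if values did prove missing, every patient with the outcome could be kept at a modest cost, using methods any trial statistician knows.

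**Step 5. What is untouched?** The primary chi-square has no covariates. Whether a chart holds an A1C does not depend on allocation, so there is no reason to expect bias between arms. G2 does not rule out unadjusted secondary comparisons.

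**The case for a change.** The strongest case for a change is that Section L is a billing list, and a billing line does not override a procedure. The baseline visit list in F2 names the medical history, which leads back to the chart-availability wording, and no study task orders a blood test. Section N records no sample collection, and the risk section mentions no blood draw. One sentence in G2 would fix the analysed set in advance. It would cost nothing if A1C proved complete, and much less than complete-case analysis if it did not.

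Part of this stands. The two sections are worded differently, and the supplied text does not prove that every patient will have an A1C. The silence of Section N and the risk section is not decisive, because a standard-care draw need not be listed in either. The Table 1 attachment cited in F1, which summarises measurements by visit, was not available and may list the test.

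What does not stand is the step from silence to harm. No rule that the plan states gives a wrong result, and no document supports any particular missing share. The choice between filling in A1C and leaving it out is also partly preference, and is easier to make once completeness is known. It can be made from the baseline data before any comparison by arm.

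**Conclusion.** No change to the plan follows. Read together, F2 and Section L most naturally provide an A1C for every patient, from the chart or from a visit 0 test, and then nothing is lost. What is left is an editorial mismatch between a procedure paragraph and a cost paragraph, and the absence of a missing-covariate rule for the secondary models of a 60-patient pilot that calls itself exploratory.

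No size of loss can be claimed. The widening of 6% to 46% in the table rests on an assumed 10% to 50% missing and on complete-case fitting, neither of which the documents state; the figure may be 0%. The r² values are assumptions too. The primary analysis is unaffected under all of them. The conclusion rests on the joint reading of F2 and Section L. If that reading failed, the result would be less precise adjusted secondary estimates, avoidable by routine analytic choices.
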